# False positive:

- 1) In subjects with localized suspected bone lesion(s) receiving targeted treatment without concomitant systemic treatment:
  - If the subject does not demonstrate a decrease of PSA by greater than 50% after targeted treatment with curative intent (ie non-palliative radiation).
- 2) If F-DCFPyL positive bone lesions do not meet the criteria for true positive findings, and appropriate correlative and follow-up imaging was acquired.

If bone lesions do not meet criteria for either true positive or false positive disease listed above, then the patient/region will be considered unevaluable for primary endpoint.

# Prostate lesions:

F-DCFPyL positive prostate bed and prostate lesions will be considered:

#### True positive:

- For patients undergoing systemic treatment (alone or in combination with targeted treatment): If on post-treatment follow-up imaging within 3-12 months, lesions seen on CT or MRI decrease by more than 30% in long axis diameter
- 2) In subjects with localized suspected lesions(s) receiving targeted treatment without concomitant systemic treatment there are two ways to meet true positive disease:
  - If the subject demonstrates a decrease of PSA by greater than 50% after targeted treatment [OR]
  - If on post-treatment follow-up imaging within 3-12 months, lesions seen on CT or MRI decrease by more than 30% in long axis diameter (with a minimum of 3 mm in change in size)
- 3) For untreated patients: If on follow-up imaging within 3-12 months, lesions seen on CT or MRI increase by more than 20% in long axis diameter (with a minimum of 3 mm in change in size).

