#### True positive:

1) For patients undergoing systemic treatment (alone or in combination with targeted treatment): If on post-treatment follow-up imaging within 3-12 months, lymph nodes seen

on CT or MRI decrease by more than 30% in short axis diameter and PSA declines by more than 50%.

- If PSA increases by more than 50% on systemic therapy, then a increase in the size of lesion by more than 20% will be considered a true positive lesion.
- 2) In subjects with localized suspected lymph node(s) receiving targeted treatment without concomitant systemic treatment there are two ways to meet true positive disease:
  - If the subject shows a decrease of PSA by greater than 50% after targeted treatment and the lymph node does not enlarge (change in size less than 20% or less than 3 mm increase in short axis diameter) [OR]
  - If on post-treatment follow-up imaging within 3-12 months, lymph nodes seen on CT or MRI decrease by more than 30% in short axis diameter (with a minimum of 3 mm in change in size)
- 3) For untreated patients: If on follow-up imaging within 3-12 months, lymph nodes seen on CT or MRI increase by more than 20% in short axis diameter (with a minimum of 3 mm in change in size).

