#### True positive:

 For patients undergoing systemic treatment (alone or in combination with targeted treatment): If on post-treatment follow-up imaging within 3-12 months, lesions seen on CT or MRI decrease by more than 30% in long axis diameter and PSA declines by more than 50%.

- If PSA increases by more than 50% on systemic therapy, then a increase in the size of lesion by more than 20% will be considered a true positive lesion.
- 2) In subjects with localized suspected lesions(s) receiving targeted treatment without concomitant systemic treatment there are two ways to meet true positive disease:
  - If the subject demonstrates a decrease of PSA by greater than 50% after targeted treatment [OR]
  - If on post-treatment follow-up imaging within 3-12 months, lesions seen on CT or MRI decrease by more than 30% in long axis diameter (with a minimum of 3 mm in change in size)
- 3) For untreated patients: If on follow-up imaging within 3-12 months, lesions seen on CT or MRI increase by more than 20% in long axis diameter (with a minimum of 3 mm in change in size).

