#### False positive:

1) For patients undergoing systemic treatment (alone or in combination with targeted treatment): If on post-treatment follow-up imaging within 3-12 months, lesions seen on CT

- or MRI increase by more than 20% in long axis diameter and PSA decreases by more than 50%.
- 2) In subjects with localized suspected lesions(s) receiving targeted treatment without concomitant systemic treatment there are two ways to meet false positive disease:
  - If the subject does not demonstrate a decrease of PSA by greater than 50% after targeted treatment [OR]
  - If on post-treatment follow-up imaging within 3-12 months, lesions seen on CT or MRI increase by more than 20% in long axis diameter (with a minimum of 3 mm in change in size)
- 3) For untreated patients: If on follow-up imaging within 3-12 months, lesions seen on CT or MRI decrease by more than 30% in long axis diameter (with a minimum of 3 mm in change in size).

If the lesion does not meet criteria for either True positive or False positive disease, then the lesion will be considered inevaluable for primary endpoint.

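### Under systemic treatment, the follow-up rule for prostate lesions departs from the node and visceral rules in two unexplained and opposing ways, so region 1 PPV is not scored on the same footing as regions 2 and 3

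*Combined protocol and SAP*

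**What the plan says.** All the rules below are in the combined protocol and SAP, section 1.1.8.4, Secondary Outcome Measurement, part A (follow-up imaging). Each is item 1 of its list, for patients on systemic treatment alone or combined with targeted treatment.

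- **Lymph nodes, true positive.** Shrinkage and a PSA fall are both required: "on CT or MRI decrease by more than 30% in short axis diameter and PSA declines by more than 50" per cent. A second branch covers progression: "If PSA increases by more than 50% on systemic therapy, then a increase in the size of lesion by more than 20" per cent, the lesion is a true positive.
- **Visceral lesions, true positive.** The structure is the same, on the long axis: "lesions seen on CT or MRI decrease by more than 30% in long axis diameter and PSA declines by more than 50" per cent, plus the progression branch, "then a increase in the size of lesion by more than 20% will be considered a true positive lesion".
- **Prostate and prostate-bed lesions, true positive.** Shrinkage alone: "lesions seen on CT or MRI decrease by more than 30% in long axis diameter". There is no PSA condition and no progression branch.
- **Prostate and prostate-bed lesions, false positive.** "or MRI increase by more than 20% in long axis diameter and PSA decreases by more than 50" per cent. Nodes and viscera have the same pairing.
- **Prostate lesions meeting neither rule.** "then the lesion will be considered inevaluable for primary endpoint". This sentence names the primary endpoint, although PPV is listed as secondary. I read it as governing PPV.

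Part C then leaves unevaluable regions out of the region analysis, ranks pathology above follow-up, and lets investigators depart from the criteria if they record it. Section 1.1.9.5 reports PPV for each blinded reader with Wilson 95% intervals.

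**The concern.** The prostate rule keeps the growth rule that yields a false positive and lacks the one that yields a true positive. A prostate lesion that grows while PSA climbs on systemic treatment is strong follow-up evidence of disease, yet without pathology it cannot be scored. The plan's own logic makes this odd: item 3 of the same list accepts growth above 20% (at least 3 mm) as true positive in untreated men, with no PSA condition.

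The same sentence is also looser than its counterparts. A prostate lesion that shrinks by more than 30% while PSA is flat or rising counts as true positive, whereas a node or visceral lesion with that course does not.

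What is at stake is the meaning of the region 1 PPV and its comparability with regions 2 and 3 of Table 1, together with the set of patients who enter the per-patient PPV. Affected men are eligible: the inclusion criteria list systemic treatment as an initial strategy and admit medically treated men having response assessed.

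**Working it through.** **Inputs.** The rules are those set out above. The documents give no expected PPV, PPV target or lesion counts, so there is no plan figure to reproduce, and every count below is an assumption.

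**Step 1: classify every combination of size and PSA change under systemic treatment, without pathology.**

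| Size change | PSA change | Node or visceral | Prostate or prostate bed |
|---|---|---|---|
| Shrinks >30% | Falls >50% | True positive | True positive |
| Shrinks >30% | Within 50% | Unevaluable | **True positive** |
| Shrinks >30% | Rises >50% | Unevaluable | **True positive** |
| Neither | Any of the three | Unevaluable | Unevaluable |
| Grows >20% | Falls >50% | False positive | False positive |
| Grows >20% | Within 50% | Unevaluable | Unevaluable |
| Grows >20% | Rises >50% | True positive | **Unevaluable** |

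Three of the nine combinations differ: two favour the prostate and one goes against it.

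**Step 2: formulas.** Take one lesion per region. Let A = shrinkage with a PSA fall >50%, h = shrinkage without that fall, g = growth with a PSA rise >50%, and F = false positives.

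- Prostate rule as written: PPV = (A + h)/(A + h + F)
- Node/visceral rule: PPV = (A + g)/(A + g + F)

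If F = 0, both are 100%. If F > 0, the prostate rule gives the lower PPV when g > h, the same when g = h, and the higher when g < h.

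**Step 3: missing growth branch alone.**

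- A + h = 30, F = 4: as written 30/34 = 88.2%. Adding g = 3, 6 or 10 gives 33/37 = 89.2%, 36/40 = 90.0% or 40/44 = 90.9%.
- A = 40, h = 0, F = 5: as written 40/45 = 88.9%. With g = 2, 5 or 10: 42/47 = 89.4%, 45/50 = 90.0% or 50/55 = 90.9%.
- A = 40, h = 0, F = 10: as written 40/50 = 80.0%. With g = 2, 5 or 10: 42/52 = 80.8%, 45/55 = 81.8% or 50/60 = 83.3%.

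The omission costs between 0.5 and 3.3 points here, roughly 1 to 3.

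**Step 4: missing PSA-decline condition alone** (A = 40, g = 0, h = 5).

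- F = 10: as written 45/55 = 81.8%, against 40/50 = 80.0% with the condition.
- F = 5: as written 45/50 = 90.0%, against 40/45 = 88.9%.

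The omission adds 1 to 2 points.

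**Step 5: both together** (A = 40, F = 10, g = 5; the node/visceral rule gives 45/55 = 81.8% throughout).

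| h | Prostate rule as written | Against node/visceral |
|---|---|---|
| 0 | 40/50 = 80.0% | Lower |
| 5 | 45/55 = 81.8% | Equal |
| 10 | 50/60 = 83.3% | Higher |

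Adding only the growth branch when g = h = 5 gives 50/60 = 83.3% against 81.8%, so half a repair leaves the regions unequal.

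**Step 6: patient level.** A man without pathology whose only PET-positive region is the prostate, and whose lesion grows with a PSA rise, meets no patient-level definition in part C and leaves the per-patient PPV. If he also has a bone lesion scored false positive on follow-up and no other true positive region, he is a false positive patient as written. With the growth branch he would be a true positive patient.

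**The case against.** **Pathology and deviations.** A reader might infer that a growing prostate lesion can never be true positive. The documents do not support that. Positive pathology makes a PET-positive lesion true positive and outranks follow-up, and part C permits recorded deviations. The gap is confined to lesions judged by follow-up. It still matters there, because histology is sought only where clinically feasible and case-by-case deviation does not replace a written rule.

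**Direction.** A reader might also infer that the rule biases region 1 PPV downward. That follows only if the missing PSA-decline condition is ignored. Counting both departures, the sign depends on whether g exceeds h, and neither count is given.

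**False positives.** The omission does not create them. Growth with a PSA fall is false positive for nodes, viscera and prostate alike; the missing branch only turns would-be true positive lesions into inevaluable ones.

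**Consequence.** PPV is a secondary endpoint with no target or hypothesis test, no comparison between regions is planned, and bone already has quite different criteria. A shift of 1 to 3 points sits well inside the Wilson interval for 30/34, about 73% to 95%. All this is correct and keeps the point small. It does not explain why two soft-tissue rules agree and the third does not.

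**Lost text.** The prostate item ends without a full stop where the visceral item continues with the PSA condition and the growth branch. Text may have been lost, but nothing marks a gap. If the approved protocol carries both clauses there, the point falls away.

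**Conclusion.** The point holds as an inconsistency in the reference standard, not as a demonstrated bias in one direction. Under systemic treatment and without pathology, the prostate rule discards growth with rising PSA and accepts shrinkage without a PSA fall, while the node and visceral rules do the opposite on both counts. No reason is stated. The first departure alone can only lower region 1 PPV or leave it unchanged; the second alone can only raise it or leave it unchanged. Each moves PPV by a few points at most on the counts tried, and neither has any effect if there are no false positives.

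The size rests on assumed counts and on one lesion per region. The differing classifications rest on the text alone. The point is minor but worth correcting, because it changes which regions and patients are counted for a named secondary endpoint.

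**What to change.** First check the prostate true positive item against the approved protocol. If the text stands as read, amend item 1 before any lesions are classified, in one edit with two parts:

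1. Add the branch already used for nodes and viscera, on the long axis: growth above 20% with a PSA increase above 50% on systemic therapy is a true positive prostate or prostate-bed lesion.
2. Add the condition of a PSA decline above 50% to the shrinkage branch, or state why it is omitted for prostate lesions.

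Making only the first change would leave every remaining difference in favour of true positive in the prostate.

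The cost is a short text amendment. It needs no new visits or data, because lesion size and PSA change are already required by the existing rules. The one drawback is that, if the PSA condition is added, some shrinking prostate lesions without a PSA fall become inevaluable, which slightly reduces the number of scored regions.

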#### False positive:

1) For patients undergoing systemic treatment (alone or in combination with targeted treatment): If on post-treatment follow-up imaging within 3-12 months, lesions seen on CT

- or MRI increase by more than 20% in long axis diameter and PSA decreases by more than 50%.
- 2) In subjects with localized suspected lesions(s) receiving targeted treatment without concomitant systemic treatment there are two ways to meet false positive disease:
  - If the subject does not demonstrate a decrease of PSA by greater than 50% after targeted treatment [OR]
  - If on post-treatment follow-up imaging within 3-12 months, lesions seen on CT or MRI increase by more than 20% in long axis diameter (with a minimum of 3 mm in change in size)
- 3) For untreated patients: If on follow-up imaging within 3-12 months, lesions seen on CT or MRI decrease by more than 30% in long axis diameter (with a minimum of 3 mm in change in size).

If the lesion does not meet criteria for either True positive or False positive disease, then the lesion will be considered inevaluable for primary endpoint.

# B) HISTOPATHOLOGY/BIOPSY:

Localization of lesions for histopathology/biopsy will be a classified by regions as specified in the miTNM framework. F-DCFPyL positive findings are aimed to be confirmed by histopathology (HP)/biopsy if clinically feasible. Pathology performed 60 days before the F-DCFPyL PET will be available for correlation. Histopathological procedures, biopsies and follow-up imaging will be performed as clinically indicated and as per institutional protocol.

The following elective procedures may guide the investigator:

Positive HP/Biopsy: Confirmed sites of metastatic or tumor involvement by histopathology/biopsy will be discussed with the responsible physician/surgeon.

- a) *True Positive*: lesion is positive on targeted biopsy/surgical sampling and is read as positive on F-DCFPvL PET.
- b) False Negative: lesion is positive on targeted biopsy/surgical sampling and is read as negative on F-DCFPyL PET.

Negative HP/Biopsy: Patients with suspected tumor recurrence on F-DCFPyL PET with negative histopathology/biopsy will be handled as outlined below:

- 1) Lymph nodes:
  - i) For patients undergoing nodal dissection: Patients will be rescanned with dedicated CT, MRI or a repeat F-DCFPyL PET to determine if the suspicious F-DCFPyL positive node was removed.
    - (1) If F-DCFPyL positive lymph node is still present, a repeat biopsy can be pursued if clinically feasible and applicable, or follow-up using imaging as described above will be performed.
    - (2) If the corresponding node was removed, then this will be considered a False Positive.

- ii) For patients undergoing needle biopsy: Images of the procedure will be reviewed to determine if the correct node was biopsied.
  - (1) If the correct node was biopsied, then a negative biopsy will be considered a False Positive.
  - (2) If the incorrect node was biopsied, then follow-up imaging as described above will be performed.
- 2) Bone lesions: Given the high rate of false negative biopsies for osseous metastases in patients with prostate cancer, patients with negative bone biopsies of PSMA PET positive lesions will be further evaluated:
  - a) If pathology demonstrates an alternative diagnoses that is known to be PSMA positive (eg Renal Cell Carcinoma metastases, Paget's disease), then this will be considered a False Positive.
  - b) If pathology is indeterminate, then follow-up imaging as described above will be performed to determine if the lesion is a True Positive or False Positive.
- 3) Although not routinely performed during standard practice, immunohistochemical staining for PSMA of tumor specimens (primary and lymph node metastases) may be performed, although not required.

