## 1.1.8 ANALYSIS SPECIFICS

# 1.1.8.1 Impact on Management Questionnaires to Referring Physicians

A pre-scan questionnaire (Q1), a post-scan questionnaire (Q2) and a follow-up questionnaire (Q3) will be used to determine whether F-DCFPyL PET/CT affected intended patient management and whether these intended treatment strategies were finally implemented. Patients can only be enrolled in the study if the pre-PET questionnaire (Q1) is completed.

The post-test questionnaire (Q2), has to be completed by the referring physician within 4 weeks after each F-DCFPyL PET/CT. The final third late follow-up questionnaire (Q3), has to be completed by the referring physician within 3 to 6 months after each F-DCFPyL PET/CT. Verification of management changes will also be done via chart review and telephone interview.

Treatment Modalities and sub-modalities will be categorized as following for modality based analysis:

- A) Surgery
- a. Prostatectomy or Prostate Bed Surgery
- b. Pelvic Lymph Node dissection
- c. Solitary LN dissection
- d. Other
- B) External radiation therapy (RT)
  - a. Prostate or Prostate Bed RT
  - b. Pelvic lymph node RT
  - c. Solitary LN Stereotactic body radiation therapy (SBRT)
  - d. Lumbo-aortic RT (standard or SBRT)
  - e. Oligo-metastasis SBRT C) Other focal therapies
  - a. HIFU
  - b. Brachytherapy

- c. Cryotherapy
- d. Other
- D) Systemic medical treatment
  - a. ADT
  - b. Chemotherapy
  - c. Immunotherapy *E*) Radionuclide therapy
  - a. bone targeted radionuclide therapy
  - b. PSMA targeted radionuclide therapy F) Watchful

waiting

Treatment management will also be categorized as follow for disease stage management based analysis:

A) Local Prostate Fossa therapy B)

Regional Pelvic therapy

- C) Lombo-aortic LN focused therapy
- D) Solitary LN or oligometastatic disease focused therapy
- E) Metastatic disease systemic therapy

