# C) DEFINITIONS OF TRUE POSITIVE, FALSE POSITIVE, TRUE NEGATIVE, AND FALSE NEGATIVE PATIENTS AND REGIONS

Pathology will be considered superior to imaging and clinical follow-up when available as described below. Patient and region level classification will be performed for each blinded reader, and be reported separately. The following criteria serve as a guide for interpretation. However not all findings on a lesions, region and patient level can be detailed here and investigators may deviate from these criteria in individual patients. These will be recorded for each interpretation that is not described in this protocol for the definition of a region or patient.

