#### 1) Patient level evaluation:

- a) *True positive patient*: A single region in a patient contains a true positive node either by pathology or imaging/clinical follow-up.
  - i) For a patient to be considered a True Positive, only one region is required to have a true positive lesion as described above, unless one region is categorized as a false positive based on pathology. This means that a single pathology false positive region outweighs regions with imaging/clinical follow-up true positive disease.
  - ii) A patient will be considered a True Positive if one region contains a lesion that is True Positive, even if other regions are categorized as inevaluable or false positive based on imaging or clinical follow-up.

- b) *True negative patient*: in the absence of True Positive or False Positive lesions, a patient will be considered a True Negative if there is pathology that is negative for disease and corresponding lesion is negative by F-DCFPyL PET.
- c) False positive patient:
  - i) Pathology confirms a false positive lesion that is read as positive on F-DCFPyL PET.
  - ii) In the absence of pathology: there are no true positive regions, and there is a region that is categorized as false positive based on imaging or clinical follow-up.
- d) False negative patient: in the absence of True Positive or False Positive lesions, a patient will be considered a False Negative if there is pathology that is positive for disease and corresponding lesion is negative by F-DCFPyL PET.
- 2) Region level evaluation: Each patient will have four evaluable regions (Table 1: prostate bed, pelvis, extrapelvic soft tissue, and bone metastases). Each region will be categorized as true positive or false positive as described above. Regions without evidence of F-DCFPyL positive disease or deemed unevaluable will not be included in the analysis.
  - a) True positive region:
    - i) Pathology confirms a F-DCFPyL avid lesion as a true positive in the region. ii) In the absence of pathology, clinical or imaging follow-up demonstrates a true positive lesion within the region independent of the presence of an inevaluable lesion or a false positive lesion (ie true positive disease will supersede a false positive lesion in the region based analysis if based on imaging/clinical follow-up).

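### A negative lymph-node specimen taken after treatment has started is still scored as a pathology false positive and can override imaging-confirmed disease in the per-patient PPV

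*Combined protocol and SAP*

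**What the plan says.** The nodal rules are in section 1.1.8.4, part 2) B) Histopathology/Biopsy, under Negative HP/Biopsy, item 1). After a dissection, repeat imaging establishes whether the PET-positive node is gone: "If the corresponding node was removed, then this will be considered a False Positive". After a needle biopsy, the procedure images are reviewed: "If the correct node was biopsied, then a negative biopsy will be considered a False Positive". Correct sampling is the only condition in either rule. The only time limit on pathology looks backwards from the scan ("Pathology performed 60 days before the" PET). No limit is set after it.

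Part 2) C) then ranks the evidence: "Pathology will be considered superior to imaging and clinical follow-up when available as described below". At patient level, "a single pathology false positive region outweighs regions with imaging/clinical follow-up true positive disease", and a patient is false positive where "Pathology confirms a false positive lesion that is read as positive on" PET, with no reference to treatment.

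The nodal imaging rules in part 2) A) do take treatment into account. They have separate branches for systemic, targeted-only and untreated patients. The first true-positive branch opens "For patients undergoing systemic treatment (alone or in combination with targeted treatment): If on post-treatment follow-up imaging within 3-12 months, lymph nodes seen" and goes on to require shrinkage above 30% with a PSA fall above 50%.

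Two provisions limit the reach of the nodal rule. Negative bone biopsies are not scored automatically: they become false positive on a PSMA-positive alternative diagnosis and go to follow-up imaging if indeterminate. Part 2) C) also calls its criteria a guide and allows recorded deviations in individual patients.

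**The concern.** Treatment changes what a later specimen can show. The plan recognises this when the reference standard is imaging, but not when it is a nodal specimen, which is the standard it ranks highest. A node that contained tumour at the scan, lost it under treatment and was then sampled would be recorded as a tracer error.

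At stake is the PPV secondary endpoint (sections 1.1.3.3 and 1.1.9.5). When the lesion was truly positive, the error runs in one direction only: PPV is too low. The patient-level ranking also lets one such node reclassify a man whose disease elsewhere was confirmed on follow-up.

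**Working it through.** The documents give no PPV target and no PPV sample size, so there is no planned figure to reproduce. The check has two parts.

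**1. The rules set side by side**, for a node that truly contained tumour at the PET and was then treated systemically:

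| What is observed | Rule applied | Score |
|---|---|---|
| Node shrinks by more than 30% on CT/MRI and PSA falls by more than 50% | Part 2) A), lymph nodes, true positive 1) | True positive |
| Same response, but the node is removed and holds no tumour | Part 2) B), item 1) i)(2) | False positive |
| Same response, but the correct node is needle-biopsied and is negative | Part 2) B), item 1) ii)(1) | False positive |

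At patient level, under part 2) C) 1):

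- Pathology false positive in one region and imaging true positive in another: **false positive** patient as written.
- The same patient with the post-treatment specimen set aside: **true positive**.
- The node is the only lesion and imaging does not resolve it: false positive as written, **unevaluable** with the specimen set aside.

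**2. Effect on per-patient PPV.** PPV = TP/(TP + FP), with N = TP + FP. Let k be the number of truly positive patients whose post-treatment negative node turns them into false positives.

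- As written: (TP − k)/N, a fall of 1/N per patient.
- Specimen set aside, disease confirmed by imaging: TP/N.
- Specimen set aside, patient unevaluable: (TP − k)/(N − k).

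Assumptions, none of them in the documents: N = 100 or 200, PPV 90% without the misclassification, k from 1 to 10.

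| N | k | As written | Confirmed by imaging | Unevaluable |
|---|---|---|---|---|
| 100 | 1 | 89/100 = 89.0% | 90.0% | 89/99 = 89.9% |
| 100 | 5 | 85/100 = 85.0% | 90.0% | 85/95 = 89.5% |
| 100 | 10 | 80/100 = 80.0% | 90.0% | 80/90 = 88.9% |
| 200 | 1 | 179/200 = 89.5% | 90.0% | 179/199 = 89.9% |
| 200 | 5 | 175/200 = 87.5% | 90.0% | 175/195 = 89.7% |
| 200 | 10 | 170/200 = 85.0% | 90.0% | 170/190 = 89.5% |

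From a starting PPV of 85%, the as-written range for k = 1 to 10 is 84% to 75% at N = 100 and 84.5% to 80% at N = 200.

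Section 1.1.9.5 specifies Wilson 95% intervals. For N = 100 and k = 5 these are 76.7–90.7% as written (85/100), 82.6–94.5% if imaging confirms disease (90/100), and 81.7–94.2% if the five are unevaluable (85/95).

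Per-region PPV changes only in the region that holds the node.

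**The case against.** **The rule is inferred from silence, and discretion exists.** No sentence says that post-treatment specimens count. The biopsy procedures are introduced as elective guidance, and part 2) C) permits recorded deviations. A reader might infer that nothing can correct such a score, and that is too strong. What stands is that nothing pre-specified corrects it: the discretion is case by case, has no criterion for this situation, and can be used after the result is known.

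**The scenario is not shown to be common.** A reader might infer that the protocol expects treatment between scan and specimen. It does not say so. Section 1.1.8.1 lists categories such as "Systemic medical treatment" without any sequence. Nor do the men in inclusion criterion 1, item 2) D) (section 1.1.4) supply the cases. They are already on treatment at the scan, so a PET-positive node without tumour may be a genuine false positive in them.

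**Reach.** A reader might extend the point to every negative specimen, but the automatic rule covers nodes only. The override is stated against imaging or clinical true positives; how a pathology true positive in another region ranks is unclear.

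**Size.** The illustration is assumed throughout. With 90/100 as the reference, 85% still lies within its Wilson interval (82.6–94.5%).

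**The obvious remedy has its own faults.** Sending every such node to imaging follow-up fails after a dissection, because a removed node cannot be measured and its absence could be misread as shrinkage. Re-routing only negatives while post-treatment positives still count pushes PPV upward. A negative post-treatment specimen also does not prove that the node ever held tumour. These objections are sound, and they shape the fix.

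**Conclusion.** The point holds for lymph nodes. As written, a negative specimen from the correct node is a false positive whatever treatment was started in between, and it outweighs imaging or clinical true-positive regions in the same patient. That is inconsistent with the treatment-dependent imaging rules beside it.

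The size is 1/N of per-patient PPV for each affected patient who would otherwise be true positive: 1 point at N = 100 and 0.5 point at N = 200. It is slightly less where the alternative is unevaluable. The direction is downward only if the lesion was truly positive. The number affected cannot be derived from the documents and may be small.

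A reader who sees the words unevaluable for primary endpoint in the follow-up criteria might infer that the main result is at risk. Section 1.1.3.3 makes management change the primary endpoint and PPV a secondary one. Section 1.1.9.5 estimates PPV without a threshold or test. This is a scoring gap that should be closed because closing it is cheap, not a threat to the trial's principal conclusion.

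**What to change.** Amend the scoring only; patient care is unaffected.

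1. In part 2) B), items 1) i)(2) and 1) ii)(1), state that a negative nodal specimen is not a pathology false positive if systemic or targeted treatment affecting that node was started or changed between the PET and the specimen. State in part 2) C) 1) that such a specimen does not trigger the patient-level override.
2. Classify that node from CT/MRI obtained before its removal or biopsy where the nodal criteria of part 2) A) can be applied, and otherwise as unevaluable. State that absence of a node after excision does not count as shrinkage.
3. Report the number of such lesions, and give PPV with Wilson 95% intervals (a) under this rule, (b) with these negatives counted as false positive, and (c) with all post-treatment nodal specimens, positive and negative, excluded from the pathology standard. Line (c) is needed because post-treatment positives still count under (a).

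The cost is a short amendment, treatment start and change dates taken from the chart review already planned (sections 1.1.8.1 and 1.1.8.4), and two extra sensitivity lines. Some lesions become unevaluable. The imaging criteria ask for follow-up at 3–12 months, so a node sampled sooner will usually fall in that group.
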